In patients with HCV infection, liver histology is a key determinant of clinical complications such as decompensation and hepatocellular carcinoma as the risk is greatest in patients with advanced fibrosis. Treatment with IFN-based therapy with or without RBV has demonstrated a delay in fibrosis progression in patients who relapse and regression of fibrosis in patients with SVR. While liver biopsy remains the reference standard, noninvasive tests such as transient elastography (FibroScan) have emerged as validated methods to evaluate degree of liver fibrosis and to monitor progression and regression of fibrosis. Whereas liver stiffness increased or did not change over time in untreated patients, patients treated with pegIFN/RBV therapy exhibited decreases in liver stiffness during and after treatment with the greatest improvements observed in patients with more advanced fibrosis at baseline.

Combinations of direct-acting antiviral agents (DAAs) targeting different steps of viral replication have the potential to significantly improve HCV treatment compared to the current interferon-containing regimens for HCV genotype 1 infection by increasing SVR rates, eliminating IFN as a component of therapy, increasing the safety and tolerability of treatment, shortening duration of therapy and simplifying the treatment algorithm. In addition, wider application of DAA therapy and better responses with combination DAA regimens could significantly reduce the public health burden of this disease.

AbbVie's IFN-free regimen for the treatment of chronic HCV genotype 1 infection includes 3 DAAs targeting different steps in HCV replication. ABT-450 is a nonstructural protein 3/nonstructural protein 4A (NS3/NS4A) protease inhibitor co-administered with the pharmacokinetic enhancer, ritonavir (ABT-450/r); ABT-267 (ombitasvir) is a NS5A inhibitor, and ABT-333 (dasabuvir) is a NS5B non-nucleoside polymerase inhibitor.

The 3-DAA regimen has been studied with and without ribavirin in over 2,300 patients in Phase 3 trials across a variety of patient populations including those with compensated cirrhosis. Based on Phase 3 data, the regimen with or without RBV appears to be safe, well tolerated and efficacious in treatment-naïve and treatment-experienced HCV

genotype 1-infected subjects including those with compensated cirrhosis. The overall efficacy results (intent-to-treat) from the Phase 3 studies are listed in [Table 1](#).

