### **Phase 3 Study in Cirrhotics: Study M13-099**

Study M13-099 is a randomized, multicenter, open-label trial in treatment-naïve subjects or subjects previously treated with pegIFN/RBV with chronic HCV genotype 1 infection with compensated (Child-Pugh A, score ≤ 6) cirrhosis. The 3 DAAs + RBV were administered for either 12 or 24 weeks of treatment.

A total of 380 subjects were randomized and received at least one dose of study drug, of which 68.7% had HCV genotype 1a, 31.3% had HCV genotype 1b, 42.1% were treatment-naïve, 36.1% were prior pegIFN/RBV null responders, 8.2% were prior pegIFN/RBV partial responders, and 13.7% were prior pegIFN/RBV relapsers.

The SVR12 rates for subjects with compensated cirrhosis treated with 3-DAA + RBV for 12 or 24 weeks were 91.8% and 95.9%, respectively. Virologic failure was noted in 13/208 (6.3%) subjects (on treatment virologic failure: n = 1; relapse: n = 12) receiving the 12-week regimen and 4/172 (2.3%) subjects (on treatment virologic failure: n = 3; relapse: n = 1) receiving the 24-week regimen.

Analyses of subgroups suggest that the overall difference in SVR12 rates was driven largely by a lower SVR12 rate among genotype 1a prior null responders who received 12 weeks of treatment, while other subgroups had comparable response rates when treated for 12 or 24 weeks. Thus, a 12-week treatment regimen is recommended for all patients with cirrhosis with the exception of genotype 1a prior null responders, for whom 24 weeks of treatment provides a higher SVR.

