4.3 Sample Size

Assuming 4% of subjects do not achieve SVR₁₂ and assuming the 5-year event rate of the composite clinical outcome is 20% in the non-SVR₁₂ subjects, with a 75% reduction in SVR₁₂ subjects (Hazard Ratio of 0.25),^{1,2} then based on two-sample log rank test (using EAST 6.0), a sample size of at least 2000 subjects enrolled in TOPAZ-I (planned to enroll 1650 subjects) and TOPAZ II (planned to enroll 600 subjects) provides greater than 80%

power to reject the null hypothesis of no difference between SVR₁₂ and non-SVR₁₂ subjects in the rate of clinical outcome events. Power calculations were based on a dropout rate of up to 20% for the hazard ratio.

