4.4 Planned Analysis

The primary analysis to evaluate the effect of response to treatment on clinical outcomes, will occur at the final analysis after all subjects have completed the study or prematurely discontinued the study. An interim analysis to assess the percentage of subjects achieving SVR₁₂ will occur after all subjects have completed the Post-Treatment Week 12 Visit or prematurely discontinued the study. For both final and interim analyses, data will be locked after performing appropriate data cleaning. Data after the interim analysis will be added to a subsequent version of the database. SAS[®] (SAS Institute, Inc., Cary, NC) for the UNIX operating system will be used for all analyses. All statistical tests and all confidence intervals will be two-sided with an α level of 0.05.

All analyses will be conducted by statisticians and statistical programmers at AbbVie or the designee according to the methodologies specified in this SAP.

There is no intention of shortening the follow-up time of subjects based on efficacy findings from the interim analysis. The intention is to follow all subjects who receive study drug for 260 weeks following treatment. There will be no statistical adjustment employed due to this interim analysis.

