10.4 Secondary Efficacy Analyses

The following analyses of secondary efficacy endpoints will be performed on the ITT-I population:

- The effect of sustained virologic response on change and percentage change from baseline in FibroScan score (assessed at the end of treatment and all post-treatment visits except PT Week 4) will be evaluated by comparing mean change from baseline at each applicable visit between subjects who achieve SVR₁₂ and those who do not using descriptive statistics and ANCOVA analyses. SVR₁₂ status will be included as a factor and baseline FibroScan score will be included as a covariate in the ANCOVA model. From the ANCOVA analyses, point estimates of the mean difference and 95% confidence intervals will be provided.
- Sustained virologic response will be evaluated using the percentage of subjects achieving SVR₁₂ (HCV RNA < LLOQ 12 weeks after the last actual dose of study drug). The simple percentage of subjects achieving SVR₁₂ will be calculated and a two-sided 95% confidence interval of the percentage will be computed based on Wilson's score method.

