The 2-sided 95% Wilson score confidence interval for a binomial proportion (percentage of subjects achieving SVR₁₂) will be produced for each subgroup with at least 10 subjects. In addition, stepwise logistic regression will be performed on both SVR₁₂ and virologic failure (on-treatment virologic failure or relapse) using subgroup variables as described above. Some variables may be treated as continuous to decrease the chance of separation or quasi-separation and some variables may be eliminated if missing for too many subjects.

For GT1 non-b subjects with cirrhosis only:

- Treatment Duration (12 weeks, 24 weeks);

The analysis on liver stiffness (change and percentage change from baseline in FibroScan score) as described in Section 10.4 will be performed on the mITT-I-GT population for the following subgroup (assessed at baseline), as appropriate:

- The presence of cirrhosis (subjects with cirrhosis vs subjects without cirrhosis);

Subgroup analyses will be performed if there are an adequate number of subjects.

The effect of subgroup status on change and percentage change from baseline in FibroScan score (assessed at the end of treatment and all post-treatment visits except PT Week 4) will be evaluated if there are at least 10 subjects in each subgroup using summary statistics and ANOVA analyses separately for each applicable visit. The subgroup status, SVR₁₂ status, and their interaction will be included in the model. From the ANOVA analyses, point estimates of the mean difference from the reference subgroup (subjects without cirrhosis) and 95% confidence intervals will be provided.

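### SAP 10.4 pools one residual variance across a roughly 4:96 SVR12 split, so its FibroScan confidence intervals can be miscalibrated

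*SAP*

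**What the plan says.** SAP 10.4 analyses "change and percentage change from baseline in FibroScan score" at end of treatment and at every post-treatment visit except Week 4, with descriptive statistics and an ANCOVA per visit. SVR12 status is the factor and "baseline FibroScan score will be included as a covariate in the ANCOVA model". From this model "point estimates of the mean difference and 95% confidence intervals will be provided". SAP 4.4 sets the level: "All statistical tests and all confidence intervals will be two-sided with an α level of 0.05". The section names no group-specific variance, robust standard error or log scale, and does not say which of the two scales governs.

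SAP 10.5 adds a cirrhosis subgroup ANOVA, in which subgroup, SVR12 status "and their interaction will be included in the model". It names no baseline covariate and makes no provision for unequal variance.

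The expected imbalance comes from SAP 4.3: "Assuming 4% of subjects do not achieve" SVR12. FibroScan is done only at sites that have it (Protocol Table 7, footnote s), and the fraction is not given.

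**The concern.** With a 4:96 split, nearly all the uncertainty in the group difference comes from the small group, while the pooled residual variance is set almost entirely by the large one. If the two residual SDs differ, the standard error is wrong.

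There is a plausible route to a larger SD in the small group. Protocol Table 4 runs from below 8.8 kPa to an open-ended F4 band, and the Protocol Introduction reports the "greatest improvements observed in patients with more advanced fibrosis at baseline". If the spread of change also grows with baseline, F4 subjects carry more variance on the kPa scale. If failures are more often cirrhotic, the non-SVR12 group has the larger SD.

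This is the analysis of the first secondary objective. A narrow interval could suggest an SVR12 effect on stiffness where there is none; a wide one could hide a real effect.

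**Working it through.** **1. The plan's own figure.** No FibroScan SD, interval width or power is stated. The only calculation built on the 4% is the primary power claim (above 80% with 2000 subjects). Inputs: SVR12 five-year risk 1 − 0.8^0.25 = 5.4%; exponential dropout of 20% over five years; 107.9 events. Schoenfeld power = Φ(√(107.9 × 0.04 × 0.96) × ln 4 − 1.96) = 80.6%. That reproduces the claim but does not bear on this point.

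**2. Group sizes.** 0.04 × 1650 = 66 non-SVR12 and 1584 SVR12. If half were scanned: 33 and 792.

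**3. F4 share among non-SVR12 subjects.** The documents do not give it, so it has to be derived.
- F4 is capped at about 400 of 1650 (24%), leaving 1250 others. Share = 400·q₄ / (400·q₄ + 1250·qₙ), where q₄ and qₙ are the failure rates.
- q₄: Protocol Table 1 weighted by the M13-099 treatment-history mix gives GT1a SVR12 of 94.5% at 24 weeks and 88.7% at 12 weeks, and GT1b 98.8% at 12 weeks.
- qₙ: the naïve rows of Table 1, 4.3% (GT1a with RBV) and 1.0% (GT1b without).
- At 50% GT1a, qₙ = 2.65%. With 24 weeks for GT1a cirrhotics, q₄ = 3.36% and the share is 13.4 / (13.4 + 33.1) = 29%. With 12 weeks for all of them, q₄ = 6.25% and the share is 25 / (25 + 33.1) = 43%.
- Across 20-69% GT1a (assumed), the share is 28-29% under 24 weeks and 38-44% under 12 weeks, against 23-24% among SVR12 subjects.
- Cross-check: the M13-099 overall rates for "compensated cirrhosis treated with 3-DAA + RBV for 12 or 24 weeks were 91.8% and 95.9" per cent imply 8.2% and 4.1% failure. Against 66 failures, 400 × 0.041 = 16.4 (25%, no enrichment) and 400 × 0.082 = 32.8 (50%).

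**4. Effect on the interval.** Let r be the residual SD ratio, non-SVR12 to SVR12. The width relative to the correct width is w = √[ s²(1/66 + 1/1584) / (r²/66 + 1/1584) ], with s² = (65r² + 1583)/1648. Coverage = 2Φ(1.96w) − 1.

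| r | w | coverage |
|---|---|---|
| 0.67 | 1.44 | 99.5% |
| 0.8 | 1.23 | 98.4% |
| 1.0 | 1.00 | 95.0% |
| 1.2 | 0.85 | 90.3% |
| 1.5 | 0.69 | 82.4% |

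Enrichment alone gives r = √[(p₁k² + 1 − p₁)/(p₀k² + 1 − p₀)], where p₁ and p₀ are the F4 shares and k is the F4 to non-F4 residual SD ratio. With k assumed to be 2 to 6, coverage is 94.1-93.0% at p₁ = 29%, 91.0-86.5% at 44% and 90.0-84.5% at 50%.

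**5. Simulation** (66 v 1584, noise proportional to baseline, no other group difference; baseline distribution assumed). Coverage:

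| F4 share of non-SVR12 | kPa, ordinary | kPa, HC3 | % change, ordinary |
|---|---|---|---|
| 24% | 94.9% | 96.0% | 94.4% |
| 29% | 92.8% | 95.0% | 94.9% |
| 40% | 89.6% | 95.0% | 94.5% |
| 50% | 85.2% | 95.2% | 95.3% |

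With 33 v 792, ordinary kPa coverage is 95.1, 92.8, 89.8 and 85.9%.

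A separate simulation with no SVR12 effect agrees. It assumed stage medians of 5.5, 9.2, 10.8 and 22 kPa, a 25% fall in both groups, and log-scale SDs of 0.15 (measurement) and 0.20 (biological). The kPa ANCOVA rejected in 4.2, 6.8, 10.4, 13.7 and 16.0% of trials at F4 shares of 24, 29, 38, 44 and 50%; HC3 rejected in 3.8-5.8%.

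**6. When the groups' relative SDs differ** (F4 share 29%). Coverage of the ordinary analysis:

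| relative SD, non-SVR12 / SVR12 | kPa | % change | log |
|---|---|---|---|
| 0.67 | 98.5% | 99.4% | 99.6% |
| 1.25 | 86.4% | 88.4% | 88.8% |
| 1.5 | 81.6% | 83.0% | 80.7% |

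HC3 stays between 94.2% and 96.0% on every scale and in every scenario of the step 5 coverage runs and this step.

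**The case against.** A reader might infer that the planned intervals are too narrow as a matter of fact. The documents do not support that, for four reasons.

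- **Both scales are planned.** Percentage change is in the same sentence as kPa change and keeps about 95% coverage when noise is proportional to baseline. That stands, though only while the groups' relative SDs are equal (step 6), and the kPa interval will be reported too.
- **Enrichment may be slight.** Protocol 5.1.2 and Table 5 assign GT1a cirrhotics to 24 weeks by default, which gives about 29% against 24% and costs one to two points of coverage. Shares of 38-50% need 12-week-type failure rates. That stands. But the Protocol allows 12 weeks where the local label does, and some subjects enrolled earlier may have finished 12 weeks, so the realised share could lie in between.
- **The direction is unknown.** The Introduction's statement about advanced fibrosis concerns mean change, not residual spread. If SVR12 subjects vary more (assumed biological SD 0.30 against 0.20), null rejection on kPa falls to 2.0% and 2.5% at F4 shares of 24% and 29%: the interval is too wide. That also stands.
- **The stakes are limited.** This is a secondary, non-randomised comparison with no multiplicity adjustment (SAP 10.2).

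Two further inferences also go too far. With no true change and 20% log-scale noise, mean percentage change is biased by exp(0.04) − 1 = 4%, but this arises in both groups and largely cancels in their difference. Nor must log kPa replace the planned scales: that changes the estimand, and by itself it does not cure unequal variance (80.7% coverage at a relative SD ratio of 1.5).

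None of this supplies the missing variance provision. The cirrhosis interaction in SAP 10.5 addresses case mix in the mean, not in the variance.

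**Conclusion.** The point holds in conditional form. As written, SAP 10.4 pools one residual variance across about 66 v 1584 subjects, so its 95% intervals are exposed to any difference in residual spread between SVR12 groups. That the safeguard is missing is clear from the text; the size and direction of the error are not.

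On the kPa scale, if spread grows with baseline stiffness and non-SVR12 subjects are enriched in F4, coverage is about 93% at a 29% F4 share and about 85-90% at 38-50%. With no enrichment and equal relative spread it is close to 95%. If SVR12 subjects vary more, it can exceed 98%. The percentage-change analysis is near nominal under proportional noise and fails in the same way as kPa if relative SDs differ. All of this rests on assumed FibroScan SDs and on an F4 share derived from Phase 3 response rates. The primary analysis is unaffected.

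**What to change.** In SAP 10.4, for both kPa change and percentage change, specify a separate residual variance for each SVR12 group (PROC MIXED with REPEATED / GROUP=SVR12) or HC3 standard errors. Either guards against error in both directions, so the unknown SDs need not be settled first.

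Add baseline fibrosis stage to the model. The Protocol's secondary objective (section 4.0) and section 8.1.2.2 ask for the effect of stage as well as of SVR12, and the exploratory PRO ANCOVA in SAP 10.9 already includes it. State which scale governs interpretation. A log-kPa analysis reported as a geometric mean ratio can be added as a sensitivity analysis.

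The cost is SAP wording and a slightly different model call, with no new data. Intervals may be wider; in the simulated case without enrichment, HC3 coverage stayed close to nominal (96.0%).

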10.5 Efficacy Subgroup Analysis

The analysis on SVR₁₂ rate as described in Section 10.4 will be performed on the ITT-I population for the following subgroups (assessed at baseline), as appropriate:

- The presence of cirrhosis and subgenotype (GT1b without cirrhosis, GT1b with compensated cirrhosis, GT1 non-b without cirrhosis, and GT1 non-b with compensated cirrhosis);
- Prior treatment history (treatment-naïve [IFN-eligible, IFN-ineligible] or IFN/RBV treatment-experienced [null responder, partial responder, relapser, prior relapse/breakthrough, prior nonresponder, IFN-intolerant and IFN experienced-other]);
- IL28B ([CC, CT, TT] and [CC or non-CC]);
- Sex (male or female);
- Age (< 55 or ≥ 55 years) and (< 65 or ≥ 65 years);
- Birth year (< 1945, 1945 to 1965, > 1965);
- Race (Black or Non-Black; Black will include any subject who marks 'Black or African American' for race on the Demographics eCRF);
- Ethnicity (Hispanic or Latino, Not Hispanic or Latino);
- BMI (< 30 or ≥ 30 kg/m²);
- Baseline HCV RNA levels (< 800,000 or ≥ 800,000 IU/mL; below median or above or equal to median);
- Baseline creatinine clearance (< 50 mL/min, ≥ 50 mL/min);
- Baseline eGFR by MDRD (< 30, 30 – 59, 60 – 89, ≥ 90 mL/min/1.73 m²; < 60 or ≥ 60 mL/min/1.73 m²);
- Baseline HOMA-IR (< 3 or ≥ 3 mU × mmol/L²);
- History of Depression or Bipolar Disorder (yes/no);
- History of Bleeding Disorders (yes/no);
- Baseline Child-Pugh score (non-cirrhotic, 5, 6, or > 6);
- Baseline fibrosis stage (F0 – F1, F2, F3, F4);
- APRI (≤ 2.0 or > 2.0);

- FIB-4 (≤ 3.25 or > 3.25); Any of APRI > 2.0 and FIB-4 > 3.25 , or neither.

For subjects with cirrhosis only:

- Baseline platelets ($< 50 \times 10^9/L$, $\geq 50 \times 10^9/L$; $< 90 \times 10^9/L$, $\geq 90 \times 10^9/L$; $< 100 \times 10^9/L$, $\geq 100 \times 10^9/L$; $< 150 \times 10^9/L$ and $\geq 150 \times 10^9/L$);
- Baseline albumin (< 35 , ≥ 35 g/L);
- Baseline alpha fetoprotein (< 20 , ≥ 20 ng/mL);
- Any of platelets $< 90 \times 10^9/L$, albumin < 35 g/L, or alpha fetoprotein ≥ 20 ng/mL, or none of the three.

The 2-sided 95% Wilson score confidence interval for a binomial proportion (percentage of subjects achieving SVR₁₂) will be produced for each subgroup with at least 10 subjects. In addition, stepwise logistic regression will be performed on both SVR₁₂ and virologic failure (on-treatment virologic failure or relapse) using subgroup variables as described above. Some variables may be treated as continuous to decrease the chance of separation or quasi-separation and some variables may be eliminated if missing for too many subjects.

For GT1 non-b subjects with cirrhosis only:

- Treatment Duration (12 weeks, 24 weeks);

The analysis on liver stiffness (change and percentage change from baseline in FibroScan score) as described in Section 10.4 will be performed on the mITT-I-GT population for the following subgroup (assessed at baseline), as appropriate:

- The presence of cirrhosis (subjects with cirrhosis vs subjects without cirrhosis);

Subgroup analyses will be performed if there are an adequate number of subjects.

The effect of subgroup status on change and percentage change from baseline in FibroScan score (assessed at the end of treatment and all post-treatment visits except PT Week 4) will be evaluated if there are at least 10 subjects in each subgroup using summary statistics and ANOVA analyses separately for each applicable visit. The subgroup status, SVR₁₂ status, and their interaction will be included in the model. From the ANOVA analyses, point estimates of the mean difference from the reference subgroup (subjects without cirrhosis) and 95% confidence intervals will be provided.

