4.2 Design Diagram

[figure not shown]
Study M14-423 is a Phase 3b, open-label, multi-center study, which is designed together with companion Study M14-222 (TOPAZ-II) to share the primary objective of assessing the effect of treatment response on long-term clinical outcomes in adults with GT1 chronic HCV infection with or without compensated cirrhosis, who are either treatment-naïve or IFN/RBV (IFN or peg IFN/RBV) treatment-experienced.

Approximately 1650 subjects will be enrolled in Study M14-423 at approximately 200 sites outside the US. The number of cirrhotic subjects (fibrosis stage of F4) will be limited to approximately 400 subjects; the number of subjects enrolled without fibrosis or with portal fibrosis without septa (fibrosis stage of F0 or F1) will be limited to approximately 1000 subjects.

As shown in [Figure 1](#), subjects meeting eligibility criteria will be enrolled to either 12 or 24 weeks of treatment according to HCV subgenotype and presence of cirrhosis. Subjects

who receive at least one dose of study drug will be followed in the Post-Treatment Period for up to 5 years (PT Week 260).

Figure 1. Study Schematic

The duration of the study will be 272 weeks (for subjects receiving a 12-week treatment) or 284 weeks (for subjects receiving a 24-week treatment), not including a screening period of up to 42 days, consisting of a 12-week or 24-week Treatment Period and a 260-week Post-Treatment (PT) Period for all subjects who receive at least one dose of study drug.

Treatment Period

Subjects who meet the eligibility criteria will be enrolled to either 12 or 24 weeks of combination therapy with or without RBV as described below and in [Table 1](#).

All HCV GT1-infected subjects who are either treatment-naïve or treatment-experienced will receive ABT-450/r/ABT-267 150/100/25 mg once daily (QD) and ABT-333 250 mg twice daily (BID). Subjects with HCV GT1a infection and all GT1-infected subjects with compensated cirrhosis will also receive RBV with weight-based dosing 1000 or 1200 mg BID.

The treatment duration will be 12 weeks for all subjects except HCV GT1a-infected subjects with compensated cirrhosis, who will receive treatment for 24 weeks, unless a treatment duration of 12 weeks is selected by the investigator based on the subject's prior

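### SAP 10.5 picks predictors of SVR12 and virologic failure stepwise from 19 overlapping variables (about 37 parameters), with no entry level stated and few events to support the selection

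*SAP*

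**What the plan says.** SAP 10.5 lists the subgroups for the SVR12 rate, each to be shown with a Wilson interval when it holds at least 10 subjects. It then adds a multivariable step: "In addition, stepwise logistic regression will be performed on both" SVR12 and "virologic failure (on-treatment virologic failure or relapse) using subgroup variables as described above". The candidates are therefore the full subgroup list.

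The list includes a four-level cirrhosis-by-subgenotype factor, fibrosis stage F0–F1 to F4, and "Baseline Child-Pugh score (non-cirrhotic, 5, 6, or > 6". Prior treatment has two naïve categories plus seven experienced ones ("null responder, partial responder, relapser, prior relapse/breakthrough, prior nonresponder, IFN-intolerant and IFN experienced-other").

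Two safeguards are given. One is coding: "Some variables may be treated as continuous to decrease the chance of separation or quasi-separation". The other is removal: "some variables may be eliminated if missing for too many subjects". Neither has a threshold.

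The SAP does not state an entry or stay level, a direction of selection, which coding applies where a variable has several, a rule for variables that duplicate each other, or any shrinkage or validation. SAP 10.2 makes no multiplicity adjustment. On size: "Approximately 1650 subjects will be enrolled in Study M14-423" (SAP 4.2), and "Assuming 4% of subjects do not achieve" SVR12 (SAP 4.3).

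**The concern.** Both outcomes are rare in this trial, and the candidate list is long and repeats itself. Stepwise selection over such a list tends to admit factors that have no effect. Among variables carrying the same information, it chooses between proxies more or less arbitrarily. Any odds ratios and intervals reported for the selected terms would make no allowance for the selection, since the SAP provides none.

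These are the SAP's only multivariable models of which patients fail the regimen. A factor named there could be read as a patient characteristic that predicts failure. Because the coding and removal rules have no thresholds, the candidate set could also be settled after outcomes are known in an open-label study.

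**Working it through.** The documents give no operating figure for this regression, so there is none to reproduce. The stated power of more than 80% concerns the primary log-rank comparison only.

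**Parameters.** Levels minus one, one coding per variable: cirrhosis-by-subgenotype 3, prior treatment 8, IL28B 2, sex 1, age 1, birth year 2, race 1, ethnicity 1, BMI 1, HCV RNA 1, creatinine clearance 1, eGFR 3, HOMA-IR 1, depression or bipolar 1, bleeding disorder 1, Child-Pugh 3, fibrosis stage 3, APRI 1, FIB-4 1. The sum is 36 over 19 variables.
- The combined APRI/FIB-4 indicator makes 37.
- The second cut-points for age and HCV RNA make 39.
- The cirrhotic-only variables (platelets 4, albumin 1, alpha fetoprotein 1, their combination 1) make 46.

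**Aliasing.** The Protocol equates cirrhosis with F4, and SAP 7.1 gives a Child-Pugh score to F4 subjects. Cirrhosis status is therefore fixed by the cirrhosis-by-subgenotype factor, by F4, and by the non-cirrhotic Child-Pugh level. Three versions of one indicator leave two redundant columns, and a rank check on a simulated design found the same two. Age and birth year, creatinine clearance and eGFR, and APRI and FIB-4 overlap strongly but not exactly. The Child-Pugh level above 6 should be almost empty, because Protocol exclusion criterion 9 bars scores of 7 or more.

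**Events.**
- SVR12 failures: 0.04 × 1650 = 66, and 66/37 = 1.8 per parameter.
- Virologic failures: the documents assume no rate for this trial. In the Phase 3 results (Protocol 3.0), non-cirrhotic GT1a with RBV had (7 + 5 + 2)/(322 + 173 + 100) = 14/595 = 2.4%. Cirrhotics had 13/208 = 6.3% at 12 weeks and 4/172 = 2.3% at 24 weeks.
- Assumptions: 400 cirrhotics (the enrolment cap), GT1b making up 30–70% of the 1250 non-cirrhotics, and essentially no failure in non-cirrhotic GT1b.
- Low end: 1250 × 0.3 × 14/595 + 400 × 4/172 = 8.8 + 9.3 = 18.
- High end: 1250 × 0.7 × 14/595 + 400 × 13/208 = 20.6 + 25.0 = 46.
- Per parameter: 18/37 = 0.5 to 46/37 = 1.2.

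**Chance that at least one factor enters when none has an effect.** For independent tests at 0.05: 1 − 0.95^19 = 62%. Overlap changes this, so forward selection was simulated with 1650 subjects and correlated covariates. The covariate distributions are assumed, because the documents give none. At least one factor enters exactly when the smallest first-step p-value is below the entry level. Each range covers 18, 33, 46 and 66 events, with 2500 runs each:

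| Candidate set | Entry 0.05 | Entry 0.10 | Entry 0.15 |
|---|---|---|---|
| 19 variables, one coding each | 57–59% | 80–83% | 91–93% |
| 22 variables, all codings | 59–62% | 82–85% | 93–95% |
| 18 variables, continuous where possible | 54–56% | 77–80% | 90–92% |
| 14 variables, overlaps pruned | 48–51% | 73–76% | 86–89% |

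The simulation error is about one percentage point: √(0.58 × 0.42/2500) = 0.01. Running the complete selection (400 runs) gave 53–61% at 0.05 for the three unpruned sets.

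The number of events hardly matters to this probability. For the 19 variables it is 58.7% with 18 events and 58.6% with 66.

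**With a true cirrhosis-by-subgenotype effect** (400 runs, entry 0.05), at least one false factor enters in 54–69% of runs if proxies of the true effect count as false, and in 44–56% if they do not.

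**The case against.** The strongest reply is that this is ordinary multiplicity over 19 unadjusted looks, which SAP 10.2 declares openly, in one supplementary sentence of a subgroup section. Failures are also described by subgroup intervals, non-response categories, relapse and breakthrough listings, and resistance analyses. All of that stands, and it limits the consequence. It does not supply the missing entry level, remove the duplicated variables, or correct estimates for selection.

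Several stronger readings are tempting but not supported:

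- A reader might infer that the low event count makes a false predictor more likely than not. The calculation shows the number of candidates does that. Few events per parameter is a separate problem, of instability and separation.
- A reader might take the 55–62% as a firm property of the plan. It needs an entry level the SAP does not state; the 0.05 in SAP 10.1 concerns treatment effects. It also assumes no true effects, whereas Protocol 3.0 reports differences by subtype, cirrhosis and prior null response.
- A reader might infer that intervals for selected terms exclude 1 by construction. A multi-level factor can enter on its joint test without any single level's interval excluding 1, and the SAP does not say which estimates will be printed.
- A reader might infer that variables are to be dropped because of separation. SAP 10.5 ties only continuous coding to separation; removal is for missing data.

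**Conclusion.** The concern holds as a weakness of a supportive analysis. As written, stepwise selection runs over about 37 partly redundant parameters, with about 66 SVR12 failures and an assumed 18 to 46 virologic failures. If no factor has an effect, the chance of at least one false entry is about 55–62% at an assumed 0.05 entry level, rising to 77–85% at 0.10 and 90–95% at 0.15 for the unpruned lists. At 0.05 it is about even when overlapping variables are pruned or when proxies of a true effect are not called false. The SAP's own option of continuous coding leaves it at 54–56%.

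These figures rest on the assumed covariate distributions and entry level. Separately, 1.8 events per parameter for SVR12, and fewer for virologic failure, make unstable estimates and separation likely. It would go too far to treat this output as the trial's main account of who fails: the primary clinical-outcome analysis, the SVR12 rate and the FibroScan analysis are untouched.

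**What to change.** Replace stepwise selection in SAP 10.5 by one pre-specified model for each of the two outcomes, fitted by Firth penalised likelihood, which handles separation without recoding after the data are seen. Report every term with its interval and label the output exploratory. Terms:

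- the SAP's four-level cirrhosis-by-subgenotype factor (3 parameters);
- prior response as naïve, null or nonresponder, or other (2);
- IL28B as CC versus non-CC (1), kept because Protocol 5.3.4 says IL28B will be analysed as a factor in response;
- baseline log10 HCV RNA, age and BMI as continuous terms (3).

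This makes 3 + 2 + 1 + 3 = 9 parameters: 66/9 = 7.3 SVR12 failures per parameter, and 18/9 = 2.0 to 46/9 = 5.1 virologic failures. Do not enter fibrosis stage F4 or Child-Pugh beside the cirrhosis factor. Leave the remaining variables in the Wilson-interval subgroup table. Pruning the list alone would not be enough, since 14 variables still give 48–51% at 0.05.

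The cost is SAP wording and some exploratory reach, because factors outside the model are shown only one at a time. The virologic failure model will still have wide intervals. A null term can still reach p < 0.05 by chance (1 − 0.95^9 = 37% for at least one of nine independent null terms), but it would appear unselected beside all the others.
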